7.2.5 Suspected unexpected serious adverse reaction

A suspected unexpected serious adverse reaction (SUSAR) is any SAE considered by the Investigator or the Sponsor to be related to the study treatment and for which the nature or severity is not consistent with the applicable reference safety information (i.e., regardless of whether the nature or severity of an SAE has been previously observed/documented).

7.2.6 Adverse events of special interest

The following are considered AEs of special interest (AESIs) for the purposes of this study, based on the known safety profiles of derazantinib and atezolizumab:

- Hyperphosphatemia/blood phosphorus increased
- Hyponatremia
- Stomatitis
- Nail disorder
- Ocular/eye disorder
- Liver function tests abnormal (compared to baseline)
- Serum creatinine increase or renal failure
- Hypertension / cardiac disorders
- QT prolongation
- Immune-related AEs (see Section 4.5.1)

All AESI must be recorded in the eCRF. In addition, immune-related AESIs, which are CTCAE grade ≥ 2 or are serious, and all other AESIs which are CTCAE grade > 2 or are serious, must be reported to the Sponsor within 24 hours using the SAE/AESI form.

7.2.7 Treatment-emergent adverse events

Treatment-emergent AEs (TEAEs) are AEs not present prior to the start of study treatment, or AEs already present prior to the start of study treatment that worsen in either intensity or frequency following the treatment.

7.3 Evaluation of adverse events

7.3.1 Grading of Severity

The severity of AEs will be assessed according to NCI CTCAE 5.0.

Adverse events not included in NCI CTCAE 5.0 should be reported under “Other” within the appropriate category, and graded 1 to 5 according to the general grade definitions:

- Grade 1: Mild AE
- Grade 2: Moderate AE
- Grade 3: Severe AE
- Grade 4: Life-threatening or disabling AE
- Grade 5: Death

For AEs that can be described by NCI CTCAE 5.0, grade 4 (life-threatening or disabling AE) is assessed based on unique clinical descriptions of severity for each AE, and these criteria may be different from those used for the assessment of AE seriousness. An AE assessed as Grade 4 based on the NCI CTCAE grades may or may not be assessed as serious based on the seriousness criteria and annotated accordingly.

7.3.2 Assessment of causality

The relationship between an AE and derazantinib and/or atezolizumab will be determined by the Investigator on the basis of their clinical judgment and following categories (see [Appendix 10](#) for definitions):

- Not related
- Unlikely related
- Possibly related
- Probably related

7.3.3 Dose-limiting toxicities (applicable to Substudies 3 and 5)

All toxicities will be graded using NCI CTCAE 5.0. Toxicities judged by the Investigator to be unrelated to study drug administration (e.g., related to the underlying disease) are not considered DLTs. In contrast, the occurrence of any of the following toxicities during Cycle 1 (DLT period) will be considered a DLT, if judged by the Investigator to be possibly or probably related to study drug administration:

1. Grade 4 non-hematologic clinical toxicity (not laboratory).
2. Grade 4 hematologic toxicity lasting ≥ 14 days with optimal supportive care.
3. Grade 3 non-hematologic toxicity (not laboratory) or non-hepatic major organ AE lasting > 3 days despite optimal supportive care with the following exceptions:
 - Grade 3 nausea, vomiting, or diarrhea that resolves to grade < 1 with or without supportive care prior to the next administration and/or with a light meal prior to derazantinib administration.
4. Any laboratory hepatic toxicity meeting Hy's law criteria for suspected severe drug-induced liver injury, defined as a rise in serum aminotransferases (AST or ALT) of $> 3 \times \text{ULN}$ and total bilirubin $\geq 2 \times \text{ULN}$, in the absence of any alternative reason (e.g., liver metastasis, another liver disease, or a concomitant drug).
5. Any grade 3 or 4 hepatic toxicity with the following exceptions:
 - For patients with grade 2 AST/ALT abnormality at baseline, an increase in the baseline abnormality to $> 10 \times$ baseline will be considered a DLT.
6. Any grade 3 non-hematologic or non-hepatic laboratory value if:
 - Medical intervention is required to treat the patient, or
 - The abnormality leads to hospitalization, or
 - The abnormality persists for > 3 days.
7. Febrile neutropenia at CTCAE grade 3 or 4:
 - CTCAE Grade 3 is defined as $\text{ANC} < 1.0 \times 10^9/\text{L}$ with a single temperature of $> 38.3^\circ\text{C}$ (101°F) or a sustained temperature of $\geq 38^\circ\text{C}$ (100.4°F) for more than one hour

- CTCAE Grade 4 is defined as ANC $< 1.0 \times 10^9/L$ with a single temperature of $>38.3^\circ C$ ($101^\circ F$) or a sustained temperature of $\geq 38^\circ C$ ($100.4^\circ F$) for more than one hour, with life-threatening consequences and urgent intervention indicated.
8. Thrombocytopenia $< 25 \times 10^9/L$ if associated with:
- A bleeding event which does not result in hemodynamic instability but requires an elective platelet transfusion, or
 - A life-threatening bleeding event which results in urgent intervention and admission to an Intensive Care Unit.
9. Grade 5 toxicity (i.e., death).
10. Any immune-related CTCAE grade 2 or higher toxicities that require holding Cycle 2 of atezolizumab administration (**Substudy 3** only, see Section 6.1.2.6).
- Note that there should be a high level of suspicion that new symptoms are treatment related, in particular any new and early immune-related toxicity.*

As dose modifications and dose titrations are not unusual with other FGFR-inhibitors, any ADRs which do not meet DLT criteria but which lead to temporary dose interruptions and/or dose reductions will contribute to the determination of the benefit-risk profile of the dose level, but will not be considered DLTs. Clinical management of ADRs is well established, and a dose reduction scheme is already provided in protocol Section 6.1.1.5.

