> 10.0 mg/dL (> 3.23 mmol/L) or significant alteration from baseline renal function or Grade 3 hypercalcemia	Withhold derazantinib with weekly reassessments until the level returns to < 5.6 mg/dL; the patient may restart at two dose levels lower, or permanently discontinue derazantinib (e.g., if considered life threatening event).
Central serious retinopathy / Retinal pigment epithelial detachment	
Grade	Action
Asymptomatic clinical or diagnostic observations only (Grade 1)	Withhold derazantinib until resolution. If the event resolves within 4 weeks, restart at the next lower dose level. If stable but not resolved for two consecutive eye examinations, restart at the next lower dose level.
Visual acuity 20/40 or better or ≤ 3 lines of decreased vision from baseline (Grade 2)	Withhold derazantinib until resolution. If the event resolves within 4 weeks, the patient may restart at the next lower dose level.
Visual acuity worse than 20/40 or > 3 lines of decreased vision from baseline (Grade 3)	Withhold derazantinib until resolution. If the event resolves within 4 weeks, the patient may restart at two dose levels lower. If the event recurs, consider permanent discontinuation of derazantinib.
Visual acuity 20/200 or worse in affected eye (Grade 4)	Permanently discontinue derazantinib.
Other events	
CTCAE grade	Action
Grade 1 or 2	Continue derazantinib at current dose, unless dose delay/modification may be clinically indicated (as assessed by the Investigator and agreed upon by the Medical Monitor or designee).
Grade 3	Withhold derazantinib until recovery to Grade 1 or baseline; administer derazantinib at the next lower dose for subsequent dosing, unless further dose reduction is required.
Grade 4	Permanently discontinue derazantinib if the event is at least possibly related to derazantinib.

Abbreviations: CTCAE, Common Terminology Criteria for Adverse Events.

6.1.1.5.1 *Hyperphosphatemia*

For all patients, it is recommended to restrict phosphate intake to 600–800 mg daily. As hyperphosphatemia is only defined by NCI CTCAE 5.0 with regards to escalating interventional measures (without specifications triggering these interventions) and not by laboratory values exceeding the upper limits of normal leading to specific interventions, [Table 5](#) guides interventions for the management of hyperphosphatemia considered at least possibly related to derazantinib.

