In alignment with interventions to ensure patient safety and for the purpose of this protocol, hyperphosphatemia is defined as:

- Grade 1: > ULN to < 7.0 mg/dL (< 2.26 mmol/L)
- Grade 2: Non-invasive intervention required (e.g., withhold drug or modify dose) or between 7.0 – 9.0 mg/dL (2.26 – 2.90 mmol/L)
- Grade 3: Severe or medically significant, but not immediately life threatening or > 9.0 – 10.0 mg/dL (> 2.90 – 3.23 mmol/L)
- Grade 4: Life-threatening consequences, urgent intervention indicated e.g., dialysis or > 10.0 mg/dL (> 3.23 mmol/L)

Patients who present with serum phosphate ≥ 7.0 mg/dL, adding an oral phosphate binding/reducing agent¹ until serum phosphate level returns to < 5.6 mg/dL should be considered, and patients should be instructed to adhere to a low-phosphate diet.

6.1.1.5.2 *Management of retinal adverse events*

A complete ophthalmological examination (see Section 5.3.2.3) should be performed by an ophthalmologist at the Screening visit, for the first four cycles (i.e., Day 1 of Cycles 2–5), and at the End of Treatment visit. Further complete ophthalmological examinations only need to be performed if clinically indicated. [Table 5](#) provides specific guidance for the management of dose delays/reductions in the case of retinal adverse events possibly related to derazantinib.

6.1.1.5.3 *Management of QTc prolongation or other significant ECG abnormalities*

If significant QTc prolongation and/or significant ventricular arrhythmia is observed, i.e., a prolonged QTcF interval ≥ 501 ms on at least two separate ECGs (mean values from triplicate ECGs, consistent with a CTCAE grade 3 event), the patient must be monitored by the Investigator and hourly (triplicate) 12-lead ECG obtained until the mean QTcF has returned to ≤ 450 msec for males or to ≤ 460 msec for females. The clinical context and possible factors contributing to QTc prolongations such as electrolyte abnormalities (potassium, calcium or magnesium), concomitant medications, or other clinical factors such as cardiac ischemia must be carefully assessed, and any findings documented in the eCRF. The decision to continue treatment with derazantinib should be reviewed and supported by a cardiologist.

¹ Either calcium-containing (e.g., calcium carbonate and calcium acetate) or non-calcium-containing (e.g., sevelamer) phosphate binders, and/or phosphaturic agents, depending on serum calcium levels and in accordance with institutional guidelines, recommendations, and schedules.

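### The DLT list in Protocol 7.3.3 is not monotone in grade: a qualifying Grade 3 non-hepatic chemistry value counts, but an isolated Grade 4 value is named by no item

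*Protocol*

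**What the plan says.** Protocol 7.3.3 lists ten DLT items for Cycle 1, all graded by CTCAE 5.0 and all requiring an event possibly or probably related to study drug. The items that bear on a non-hepatic chemistry value are these:

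- Item 1: "Grade 4 non-hematologic clinical toxicity (not laboratory" being its closing restriction.
- Item 2: "Grade 4 hematologic toxicity lasting ≥ 14 days with optimal supportive care".
- Item 3: "Grade 3 non-hematologic toxicity (not laboratory) or non-hepatic major organ AE lasting > 3 days despite optimal supportive care", with exceptions for nausea, vomiting and diarrhea.
- Item 5: "Any grade 3 or 4 hepatic toxicity with the following exceptions".
- Item 6: "Any grade 3 non-hematologic or non-hepatic laboratory value if" it requires medical intervention, leads to hospitalization or persists for more than 3 days.
- Item 10 (Substudy 3 only): immune-related toxicity of Grade 2 or above that requires Cycle 2 atezolizumab to be held.

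The remaining items cover Hy's law (4), febrile neutropenia (7), thrombocytopenia with bleeding (8) and death (9). SAP 6.4.1 adds no definition of its own and refers back to the protocol list.

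The DLT proportion is the primary safety endpoint of the safety interim analysis (SIA) in both substudies (Protocol 3.2.1.2). DLT incidence is also the only outcome in the dose-toxicity model (Protocol 8.3.5.1, SAP 6.4.2), which declares a dose unacceptable when the posterior probability of a DLT rate of 25% or more exceeds 25%.

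**The concern.** A toxicity definition should not lose an event because it became more severe. Here a related chemistry abnormality that lasts four days at Grade 3 is a DLT, while the same abnormality at Grade 4, without a clinical event, is named nowhere. No reason is given, so this looks like a drafting slip.

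It falls on toxicities the protocol itself singles out. Hyponatremia, creatinine increase and hyperphosphatemia are listed as important potential risks of derazantinib (7.1.1.2) and as adverse events of special interest (7.2.6). The SIA exists to judge a higher daily dose than the 300 mg used so far in this study. Compared with a list that treats Grade 4 at least as strictly as Grade 3, the omission acts in one direction only: it can lower the DLT count and never raise it. With 10 patients per substudy, one patient is 10 percentage points of the endpoint.

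**Working it through.** **Coverage of the list.** Take a study-drug-related laboratory value that is neither hematologic nor hepatic, and read each item literally.

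| Grade | Item that names it |
|---|---|
| 3, with intervention, hospitalization or >3 days | 6 |
| 4, no Grade 4 clinical event | none (item 10 in Substudy 3, if immune-related and Cycle 2 atezolizumab is held) |
| 5 | 9 |

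Grade 3 in item 6 cannot safely be read as Grade 3 or higher. The same list names Grades 3 and 4 together in items 5 and 7, and writes Grade 2 or higher in item 10. Where the authors wanted a range, they wrote one.

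**What one patient is worth in the model.** The documents state no figure to reproduce, so this is an illustration. Inputs from Protocol 8.3.5.1:

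- logit(π_d) = log(α_i) + β·log(d/600), with i = 1 for monotherapy and i = 2 for combination.
- Independent normal priors on log(α₁), log(α₂), log(β): means −1.386, −1.386, −0.781; SDs 5.472, 5.472, 0.973.
- At 400 mg/day, log(400/600) = −0.405. Overdosing is π ≥ 0.25, that is logit(π) ≥ log(0.25/0.75) = −1.099.
- 10 patients at 400 mg/day, y of them with a DLT.

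Dose history given in the documents: combination 0/7 at 200 mg and 0/6 at 300 mg (Protocol 1.4.1.2); monotherapy 0/12 at 400 mg (Protocol 7.1.1.1).

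Posterior P(π ≥ 0.25) at 400 mg/day, by grid integration, against the limit of 0.25:

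| Setting and history used | Last acceptable count | First unacceptable count |
|---|---|---|
| Combination; 0/7 and 0/6 | 3/10: 0.16 | 4/10: 0.37 |
| Combination; also 0/12 monotherapy | 3/10: 0.17 | 4/10: 0.39 |
| Monotherapy; 0/12 | 4/10: 0.19 | 5/10: 0.36 |
| Monotherapy; no history | 1/10: 0.08 | 2/10: 0.30 |

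Integration by simulation moves these by about 0.01 and changes no classification. In each row, one uncounted patient at the boundary separates an acceptable from an unacceptable model result.

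**The case against.** The strongest reply is that few events fall through and that nothing is hidden from those who decide. Much of that stands.

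- **Other routes into the list.** In Substudy 3, item 10 can catch immune-related lipase or renal events, because Appendix 4 withholds or stops atezolizumab for them. A Grade 4 value with a Grade 4 clinical syndrome counts under item 1, and Protocol 7.4.3.1.1 asks for the clinical syndrome to be recorded where appropriate. The second limb of item 3 (major organ events) might be read to take a sustained renal event. An investigator might also count a value because it passed through Grade 3, but the text does not say so and sites could differ. What remains is the isolated Grade 4 chemistry value, mainly in Substudy 5.
- **Other safety review.** The SIA conclusion is a joint decision of the IDMC, investigators and sponsor on DLT, AE and PK data (Protocol 8.3.5.1). Serious events of special interest, and those above Grade 2, reach the sponsor within 24 hours (7.2.6).

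A reader might also infer four stronger things that the documents do not support.

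- **That a phosphate above 10.0 mg/dL is certainly an uncounted Grade 4.** The protocol scale in 6.1.1.5.1 has "Grade 4: Life-threatening consequences, urgent intervention indicated e.g., dialysis or > 10.0 mg/dL", but 7.3.3 grades by CTCAE 5.0, which 6.1.1.5.1 says does not define hyperphosphatemia by laboratory values. Which scale governs DLTs is unresolved.
- **That 7.3.3 confirms the exclusion** where it says that "any ADRs which do not meet DLT criteria but which lead to temporary dose interruptions and/or dose reductions will contribute" to the benefit-risk assessment and are not DLTs. That sentence concerns temporary interruptions and reductions. The gap rests on the list itself.
- **That Table 5 contradicts the list** because its Grade 4 row for other events says "Permanently discontinue derazantinib if the event is at least possibly related to derazantinib". That row is a dosing rule, and phosphate has its own row with more than one outcome. Dosing rules and DLT items differ elsewhere too: a Grade 4 hematologic event shorter than 14 days is not a DLT under item 2.
- **That one missed patient would reverse the SIA decision.** It would reverse the model result, and only if the count is already at the boundary.

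**Conclusion.** The inconsistency is real and can be read directly from 7.3.3. An isolated, related Grade 4 non-hepatic chemistry value is left out of the primary safety endpoint and the model, while its qualifying Grade 3 counterpart is included. Its expected size cannot be stated, because the documents give no frequency for such values. Its possible size is one step in the DLT count per affected patient, which at the boundary carries the overdose probability across 0.25.

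The model figures rest on three assumptions: dose enters as total daily dose; DLTs in the earlier cohorts can be pooled with those defined here; and the history shown is complete enough to illustrate. The last is known to be imperfect, since 7.1.1.1 reports DLTs at 250 mg and 425 mg without counts. The monotherapy boundary moves from between 1/10 and 2/10 to between 4/10 and 5/10 according to whether the 0/12 is used. The coverage finding depends on none of this.

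**What to change.** - Reconcile items 1 and 6 of Protocol 7.3.3, so that the classification of Grade 4 non-hepatic laboratory values is explicit and consistent with that of Grade 3 values.
- Reconcile the CTCAE 5.0 grading in 7.3.3 with the phosphate grades in 6.1.1.5.1, and state which applies when DLTs are assessed.
- Classify all SIA patients against the reconciled list before the model is run.

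How these values should be classified clinically is for the sponsor and its safety advisers; the statistical requirement is one consistent, pre-stated rule. The cost is a short wording change in an amendment, which SAP 6.4.1 must then cite, and review of up to 20 patients (10 per substudy). The Cycle 1 laboratory samples are already in the schedule (Table 1), so no new data are needed. If Grade 4 values are brought in, the DLT count can stay the same or rise.

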7.4 Handling of safety information and collection periods

7.4.1 Responsibilities and procedures

The responsibility for the safety of an individual patient lies in all cases with the Investigator. This includes the timely review of all safety data obtained during the course of the study.

An Investigator must instruct their patients to report any AE and SAE they experience.

7.4.2 Handling of safety data during the pre-treatment period

Any relevant change in, or worsening of, a patient's condition occurring after any informed consent has been provided but prior to the start of first study-drug administration, is to be recorded in the eCRF as pre-dose medical history (see Section 5.3.1.1). However, in this period (between ICF and start of study medication), if an AE/SAE is assessed as related to the study procedure, the AE/SAE is to be reported accordingly in the eCRF as medical history and, in addition, SAE must also be reported to the Sponsor's safety representative, using the same procedures as for an SAE (see Section 7.4.3.2).

7.4.3 Handling of safety data during the treatment period and up to the last scheduled follow-up

From the start of first dosing up to and including the Safety Follow-Up visits 28 and – if applicable – 90 days after last study drug administration, respectively, any change in, or worsening of, a patient's condition must be collected and reported in the eCRF as an AE (see Section 7.4.3.1). Serious adverse events and AESIs must be additionally reported on the SAE/AESI report form (see Section 7.4.3.2).

7.4.3.1 Adverse event management

7.4.3.1.1 Data collection

All AEs directly observed (physical examination, laboratory test or other assessments), mentioned by the patient, or reported by the patient upon non-directive questioning, must be recorded on the AE pages of the eCRF.

All AEs must be recorded in the English language in the eCRF and should include the following information:

- Term. If possible, a diagnosis should be documented rather than signs and symptoms, using self-explanatory and concise medical terminology. However, if an observed or reported sign or symptom is not considered a component of a specific disease or syndrome by the Investigator, it should be recorded as a separate AE. Progression of disease is considered an efficacy outcome parameter and should not be captured as an AE or SAE, unless its outcome is death.
- Duration (start and end dates).
- Toxicity grade (CTCAE grade; see Section 7.3.1).
- Relationship to the study treatment (causality assessment; see Section 7.3.2).
- Action(s) taken with regards to study drugs (derazantinib and atezolizumab), or any suspected concomitant medication
- Additional treatments given for the event.
- Whether it is an SAE (seriousness assessment; see Section 7.2.2).
- Outcome.

Refer to the eCRF completion guidelines for further details on completing the AE/AESI/SAE in the eCRF.

In addition, the concomitant medications (with indication start and stop (if not ongoing) and Medical history should be updated as needed.

Abnormal laboratory results should not be recorded as an AE unless the abnormal result meets one or more of the following criteria:

- induces clinical signs or symptoms which require therapy or additional diagnostic evaluation
- requires dose modification derazantinib, or discontinuation of study participation
- is considered clinically significant

If a laboratory abnormality meets one of the above criteria, the clinical syndrome associated with laboratory abnormality is to be recorded, as appropriate (e.g., diabetes mellitus instead of hyperglycemia).

AEs must also be reported in the source document with at least the nature of the event, the start and end date, the relationship to the study drugs (derazantinib and/or atezolizumab), treatment (if applicable), and outcome (in initial or follow up report).

7.4.3.1.2 *Follow-up*

Once an AE is detected, it must be proactively followed at each visit (or more frequently if necessary) for any changes in severity, relationship to the study drug, interventions required for treatment, and the event's outcome. Refer to the eCRF completion guidelines for further details on completing the AE/AESI/SAE in the eCRF.

All AEs must be followed-up until they have returned to baseline status or have stabilized, or until the scheduled Safety Follow-Up visit(s).

Unless the patient withdraws their consent, unresolved related AEs and both related and unrelated SAEs at the time of the Safety Follow-Up visit(s) will be followed until they have, in the opinion of the Investigator, resolved to baseline, CTCAE grade 1, stabilized, or are deemed to be irreversible (including death) and .

7.4.3.2 *Serious adverse event and AESI reporting*

7.4.3.2.1 *Investigators responsibility*

In addition to being reported and followed-up as AEs (see Section 7.4.3.1), SAEs and AESIs meeting expedited reporting criteria (see Section 7.2.6) must be reported to the Sponsor's safety representative listed below, within 24 h of awareness of the event.

In addition to SAE/AESI form completion, such reports might include detailed anonymized descriptions (e.g., discharge letter, autopsy report, etc.) and/or relevant data (e.g., ECG, laboratory tests, discharge summaries, postmortem results, etc.). If any questions or considerations regarding an SAE or AESI arise, the Sponsor's Medical Monitor or designee should be consulted.

Safety Vendor	Sponsor's Medical Monitor
[REDACTED]	[REDACTED]

The information provided in an SAE/AESI report should be as complete as possible, but contain a minimum of:

- A short description of the AE (diagnosis) and the reason why the AE was categorized as serious or reportable AESI
- Patient identification and treatment (if applicable)
- Investigator's name and phone number (if applicable)
- Name of the suspect study drug and dates of administration
- Assessment of causality

If all information about the SAE or AESI is not yet known, the Investigator will be required to report any additional information within 24 hours as it becomes available.

The Investigators must in turn notify their governing IRB/IEC in line with local requirements. This activity may be delegated.

